## **5.2 Study Population**

### **5.2.1 Subject Selection**

Adult male and female patients will be consecutively screened for the study. Eligible patients must meet all of the inclusion criteria and none of the exclusion criteria.

### **5.3 Withdrawal and Lost to Follow Up**

Subjects may be withdrawn from the study for any of the following reasons:

- Lost-to-follow up despite exhaustive attempts to contact. A minimum of three (3) attempts to contact such subjects must be made. One such attempt must include a registered return receipt requested letter. All attempts to contact the subjects must be documented.
- Subjects may voluntarily decide to withdraw from the study. All reasonable attempts should be made to ascertain the reason for voluntary withdrawal.

All subject withdrawals must be documented on the **Study Completion/Exit Case Report Form (eCRF)**.

### **5.4 Duration of the Study**

Subject follow-up visits will occur at 1, 6, and 12 months post implant procedure.

## **5.5 Conduct of the Study**

### **5.5.1 Schedule of Activities**

Treatment of subjects enrolled in this study will include all tests and procedures listed in the Schedule of Activities in Appendix IV. Placement of the AAA stent graft will be performed in accordance with the IFU.

#### **5.5.1.1 Patient Screening**

Prospective subjects are consecutively evaluated for study eligibility at the time they are considered for AAA repair. Initial screening may include diagnostic testing (e.g., imaging, angiogram, laboratory testing) performed as part of routine medical care.

The following steps outline the process to determine patient eligibility for enrollment and subsequent shipment of the device(s):

1. Ensure that patient has signed an IRB/EC approved Informed Consent Form, per Institutional policies
2. Submit contrasted spiral CT images of slice thickness  $\leq 3$  mm to the Sponsor obtained within 6 months of anticipated treatment.

#### **5.5.1.2 Pre-procedure Evaluation**

The following assessments will be performed no more than one month prior to the implant/surgical procedure:

- Patient demographics
- Medical/surgical history
- Physical exam
- Ankle-Brachial Index (ABI)
- Laboratory testing, which includes renal assessment and serum pregnancy for female patients of childbearing potential.

If the patient is eligible to be enrolled into the study, the results of these screening assessments are recorded on the **Baseline eCRF**. If a patient is not enrolled into the study, the baseline screening worksheets will be retained, together with the patient's signed/dated consent(s).

#### **5.5.1.3 Treatment Period (implant/surgical procedure)**

The following assessments and data collection will be performed at the time of the implant/surgical procedure:

- Device accountability- documentation of product information (e.g., lot number, serial number, and expiration date).
- Type and length of anesthesia
- Type of vascular access (e.g. femoral cut down or percutaneous)
- Estimated blood loss
- Adjunctive procedures (e.g. stent placement)
- Investigator assessment of AAA device performance as it relates to delivery/deployment/required interventions, endoleak, and device integrity issues
- Procedural times (total device and procedure)
- Fluoroscopy time

- Contrast medium volume
- Adverse events
- The above assessments are recorded in the **Procedure eCRF**.

#### 5.5.1.4 *Pre-Discharge*

The following assessments and testing will be performed post-procedure, prior to discharge:

- Physical exam
- Length of hospital stay
- ICU stay
- Adverse events
- KUB X-ray (AP, lateral, left oblique and right oblique views)

The above assessments are recorded in the **Discharge eCRF**. In some instances, subjects may experience a prolonged hospitalization post procedure. In those cases, the above assessments should be performed no more than two (2) weeks post procedure.

#### 5.5.1.5 *Post-Treatment Follow-up Period*

The following assessments and tests will be performed at the following intervals:

Time period post-treatment	Acceptable visit timeframe allowance
1 Month (30 days)	± 14 days
6 Months (180 days)	± 30 days
12 Months (365 days)	± 60 days

- Physical exam
- Laboratory test, which includes renal assessment at 1-month follow-up visit
- Contrast Enhanced Spiral Abdominal/Pelvic CT and X-ray (KUB), to be evaluated by Independent Core Lab
- Adverse events

The above assessments are recorded in the appropriate **Follow-up Visit eCRF**. Note that in the event the subject is unable to tolerate a contrast-enhanced spiral CT, a duplex ultrasound and non-contrast spiral CT should be completed as an alternative assessment.

#### 5.5.1.6 *Unscheduled Follow-up Visits*

In the event that a subject visit occurs outside the protocol-specified time frames (i.e., Pre-discharge, 1 month, 6 months, 12 months) sites are required to record data from that visit, if that visit is specifically associated with the device, procedure or aneurysmal disease. Possible reasons for unscheduled visit data collection may be:

- Subject experiences new symptomatology and/or an adverse event
- Surveillance of an existing adverse event

The Unscheduled visit information would be recorded in the **Unscheduled Follow-up Visit eCRF** where the reason for the unscheduled visit will be specified.

If a subject is seen in the office or clinic for other reasons than listed above, information from that visit would be recorded on the next protocol-specified visit in the appropriate **Follow-Up Visit eCRF**.

**5.5.1.7**                      ***Discontinuation from Study***

Subjects who choose to discontinue participation in the study prior to study completion will be requested to undergo a final assessment by the investigator at the time notification is made of their decision to discontinue. If the subject notifies the clinical site of discontinuation by mail or phone, subject will be requested to have a final assessment by the investigator.

The final assessment will be recorded in the **Follow-up Visit** and **Study Completion/Exit eCRFs**.

---

## 6.0 DEFINITIONS

The outcomes defined below will be collected by the study sites and evaluated by the Independent Core Lab as specified.

### 6.1 *Endoleak*

Endoleak is evaluated by the Independent Core Lab and is defined by the persistence of blood flow outside the lumen of the endovascular graft but within the aneurysm sac and can be classified as:

- *Type I* – Ineffective seal at either the proximal or distal sealing zones
    - *Type IA* – Ineffective seal at the proximal sealing zone
    - *Type IB* – Ineffective seal at the distal sealing zone
  - *Type II* – Retrograde blood flow from lumbar arteries, the inferior mesenteric artery, or other collateral vessels into the aneurysm sac
  - *Type III* – A leak caused by fabric tears or disruption, component disconnection, or graft disintegration
  - *Type IIIA* - Junctional leak or component disconnection
  - *Type IIIB* - Midgraft hole
  - *Type IV* – Blood flow through an intact fabric.
  - *Unknown endoleak* - Endoleak present but unable to assess type
- Endoleak will only be evaluated as an adverse event or serious adverse event if it is present at the 30-day follow-up visit or if a post-index procedure re-intervention occurs.

### 6.2 *Migration*

Migration is evaluated by the Independent Core Lab and is defined as evidence of proximal or distal movement of the stent graft >10mm relative to fixed anatomic landmarks. Spiral CT images will be used to determine migration at regularly scheduled follow-up visits. The 1 month image will be used as the baseline assessment.

### 6.3 *Patency*

Patency is defined as the absence of complete occlusion (100%) of the device or native vessel. Patency can be either within the device (device patency) or the native vessel outside the device (vessel patency). This may be evidenced by: CT, angiography, ultrasound or other imaging modality, or pathological analysis.

### 6.4 *Thrombosis*

Thrombosis is defined as complete occlusion (100%) of the device or native vessel. Thrombosis can be either within the device (device thrombosis) or the native vessel outside the device treatment area (vessel thrombosis). This may be evidenced by: CT, angiography, ultrasound or other imaging modality, or pathological analysis.

### 6.5 *Stenosis*

Stenosis is defined as narrowing of the blood flow lumen that is less than 100% occlusion. Stenosis can be either within the device (device stenosis) or the native vessel outside the device treatment area (vessel stenosis). This may be evidenced by: CT, angiography, ultrasound or other imaging modality, or pathological analysis.

### **6.6 Loss of Stent Graft Integrity**

The integrity of the stent graft is evaluated by the Independent Core Lab via abdominal X-rays at regularly scheduled follow-up visits. Any fractured stents, and any other issues compromising the integrity of the stent graft will be reported.

### **6.7 AAA Enlargement**

Aneurysm enlargement is evaluated by the Independent Core Lab and is defined as a greater than 5 mm (diameter) increase in the aneurysm size. Spiral CT images will be used to determine aneurysm enlargement at regularly scheduled follow-up visits. The 1 month image will be used as the baseline assessment. In addition, aneurysm volume will be assessed by the Independent Core Lab and reported in the data analysis, but diameter is considered the relevant characteristic for the study endpoint evaluations.

### **6.8 Surgical Conversion**

Surgical conversion occurs when a subject implanted with an Ovation Alto Abdominal Stent Graft undergoes open surgical repair with explantation of the stent graft. The follow-up for subjects who are converted to open surgical repair include collection of the following data: Physical Exam and assessment of Adverse Events. The visits are to occur at 1 month post open conversion. The patient will remain enrolled in the study until 30 days after the conversion procedure or the discharge date of the conversion procedure, whichever occurs later.

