- AAA-related mortality\*\*\*
- Device-related AEs & SAEs\*\*\*
- Major Adverse Events (MAE)\*\*\*
- Loss of patency
- Stent fracture
- Thromboembolic event (deep vein thrombosis, pulmonary embolism, embolic stroke, limb ischemia)

\*\*\*These assessments will be reported at 12 months in addition to the 12-month Primary Effectiveness endpoints listed above. MAEs and device-related SAEs will be adjudicated by the Clinical Events Committee (CEC) at 1, 6 and 12 months.

MAE is defined as:

- All-cause mortality: any death occurring during the study period, regardless of cause
- Myocardial infarction: the presence of raised levels of one or more cardiac biomarkers in comparison to local laboratory reference ranges
- Stroke (excludes TIA) : a sudden development of neurological deficit due to vascular lesions of the brain such as hemorrhage, embolism, or thrombosis that persists for >24 hours
- Renal failure (excludes renal insufficiency): the need for temporary or permanent dialysis
- Respiratory failure (excludes COPD or pulmonary complications): pneumonia or respiratory failure requiring ventilator support beyond 24 hours post-procedure
- Paralysis (excludes paraparesis): paralysis of the lower extremities inclusive of the lower trunk
- Bowel ischemia: the lack of adequate blood flow to the intestines that requires intensification of medical therapy or surgical/endovascular intervention
- Procedural blood loss ( $\geq 1,000$  mL): estimated blood loss during the index procedure  $\geq 1,000$  mL

---

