### ***6.15 Conversion to Open Surgical Repair***

Conversion to open surgical repair may occur either at the initial implant procedure or subsequent to the initial procedure. Information regarding the surgical conversion will be recorded on the Procedure eCRF (if at initial implant) or Follow Up eCRF (after implant), and the **Adverse Event eCRF/ Secondary Intervention eCRF**.

In the event that a subject requires conversion from endovascular to open surgical repair, the explanted device should be sent to the Sponsor for examination. Refer to **Appendix VI** for specific instructions for managing the removal, shipping and handling of the explanted device. Explant information will be recorded on the **Secondary Intervention eCRF under Adverse Event eCRF**.

Surgical conversions must be reported by telephone, email or EDC system by noting an Adverse event/secondary intervention to the study Sponsor **within 24 hours** of knowledge of the event.

The Follow-up visit schedule for surgically converted subjects is at one month post open conversion.

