### 7.2 *Additional Study Evaluation*

Additional assessments that will be reported at each follow-up interval include:

- Type I endoleak, to be assessed by an Independent Core Lab
- Type III endoleak, to be assessed by an Independent Core Lab
- Stent graft migration > 10 mm (compared to 1-month baseline), to be assessed by an Independent Core Lab
- AAA enlargement > 5 mm (compared to 1-month baseline)
- Loss of patency
- Stent fracture, to be assessed by an Independent Core Lab
- AAA rupture
- Conversion to open repair

- Secondary interventions
- AAA-related mortality
- Adverse events, including:
  - Serious adverse events
  - Major adverse events
  - Procedure-related adverse events
  - Device-related adverse events
  - All adverse events, regardless of seriousness or cause

All deaths that occur in the study will be adjudicated by the CEC. AAA related death is any death determined by the CEC to occur as a result of the initial procedure (first 30 days), AAA rupture, conversion to open surgical repair, or any AAA related secondary intervention.

---

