## 8.0 DATA ANALYSIS

### 8.1 *Analysis Population*

Primary analyses will be performed on a modified intent-to-treat basis. The modified intent-to-treat group includes all subjects in which the delivery system was inserted into an access vessel. All subjects who achieve technical success and remain free of all other elements of the composite effectiveness endpoint at 12 months will be considered treatment successes. All subjects who fail based on any element of the composite effectiveness endpoint, and all subjects who deemed treatment successes will be included in the denominator. Only subjects with readable imaging during each respective follow-up interval will be included in the denominator for relevant effectiveness endpoints. Subjects not counted as failures, but with incomplete data to assess all the composite elements will be treated as missing data points.

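### Subjects converted to open repair leave the study about 30 days after conversion, so the 12-month mortality and MAE summaries may miss their later events

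*Combined protocol and SAP*

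**What the plan says.** Section 6.8 sets the exit rule for a converted subject: "The patient will remain enrolled in the study until 30 days after the conversion procedure". The full clause lets a long hospital stay delay the exit, since enrolment lasts "until 30 days after the conversion procedure or the discharge date of the conversion procedure, whichever occurs later". Follow-up in that interval is a physical exam and adverse event assessment, and "The visits are to occur at 1 month post open conversion". Section 6.15 gives the same schedule: "The Follow-up visit schedule for surgically converted subjects is at one month post open conversion".

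The safety reporting runs longer than this. For secondary interventions, AAA-related mortality, device-related events and MAE, section 1.0 states: "These assessments will be reported at 12 months in addition to the 12-month Primary Effectiveness endpoints listed above". Death is an MAE component, defined in section 1.0 as "All-cause mortality: any death occurring during the study period, regardless of cause". Sections 6.13 and 11.2 refer to a one-year MAE safety endpoint, and section 5.0 makes safety through 12-month follow-up a secondary objective. Section 7.2 includes among AAA-related deaths those that the Clinical Events Committee attributes to "AAA rupture, conversion to open surgical repair, or any AAA related secondary intervention". Its 30-day limit is attached only to the initial procedure.

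On the effectiveness side, section 7.1 makes conversion a failure of the composite, and section 8.1 keeps failures in the denominator. Section 8.4 makes all outcomes other than the primary one descriptive.

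**The concern.** The follow-up rule and the reporting horizon do not match. A subject converted on day 60 normally leaves at about day 90. If that subject dies on day 150 from a consequence of the conversion, the death meets the section 7.2 definition and falls inside the 12-month horizon, but no procedure would bring it into the database.

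Nothing elsewhere closes the gap. Section 6.17 requires deaths to be reported while the study is being conducted, but sets up no vital-status check after an exit that the protocol itself directs. Section 5.3 lists loss to follow-up and voluntary withdrawal as withdrawal reasons and does not mention exit after conversion. The missing-data rules in sections 8.1 and 8.3 deal with the effectiveness endpoints, and the planned sensitivity analyses concern only the primary endpoint.

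This is a single-arm study, so its descriptive 12-month mortality and MAE rates are its one-year safety evidence. Loss of observation that follows a treatment-failure event is unlikely to be independent of later risk, and there is no control arm with the same loss to compare against.

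**Working it through.** **1. The primary endpoint is untouched.** Inputs from section 8.5: 60 evaluable subjects, goal 80%, assumed success 92.8%, one-sided exact 95% limit, stated power 86.1%.
- P(X ≥ 53 | 60, 0.80) = 0.0670, above 0.05. P(X ≥ 54 | 60, 0.80) = 0.0308, so success needs 54 of 60.
- Power = P(X ≥ 54 | 60, 0.928) = 0.8611, which reproduces the stated 86.1%.
- 75 enrolled corresponds to 20% attrition: 60 / (1 − 0.20) = 75.

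A converted subject is already a failure in the denominator. Longer follow-up changes none of these figures.

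**2. How much of the year is lost.** Inputs: exit 30 days after conversion (section 6.8, assuming discharge by then) and a 12-month horizon at day 365 (section 5.5.1.5). For conversion on day d, days lost = 365 − min(365, d + 30).

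| Conversion day | Exit day | Days lost | Share of year |
|---|---|---|---|
| 0 | 30 | 335 | 92% |
| 30 | 60 | 305 | 84% |
| 90 | 120 | 245 | 67% |
| 180 | 210 | 155 | 42% |
| 270 | 300 | 65 | 18% |
| 335 | 365 | 0 | 0% |

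The 12-month analysis window opens on day 305 (section 8.2). A conversion before day 305 − 30 = 275 therefore ends observation before that window opens. A conversion from day 335 on loses nothing up to day 365.

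**3. Largest effect on a crude rate.** The documents give no conversion rate, so assume k = 1 to 3 early conversions among 75. If each converted subject has an unseen death, or an unseen first MAE, and is counted as event-free, the undercount is k/75:
- k = 1: 1/75 = 1.3 points
- k = 2: 2/75 = 2.7 points
- k = 3: 3/75 = 4.0 points

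For example, a reported 1/75 (1.3%, exact 95% CI 0.03 to 7.2%) would have been 2/75 (2.7%, 0.3 to 9.3%).

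**4. Expected effect.** With probability q of an unseen event per converted subject, the expected undercount is k × q/75. As an illustrative range take q = 5% to 50%, the approximate elective and emergent open-repair mortality figures in section 2.1.2.
- k = 1: 0.07 to 0.67 points
- k = 3: 0.2 to 2.0 points

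Those figures describe operative mortality, much of which would fall before exit. Risk after exit may therefore be lower than this range suggests.

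**5. Direction depends on the denominator rule.** Suppose one subject converts and one event is seen in another subject. Counting the converted subject as event-free reports 1/75 = 1.33%. Dropping that subject reports 1/74 = 1.35%. The true figure is 1/75 = 1.33% if the converted subject stays event-free and 2/75 = 2.67% if not. The plan does not say which rule applies.

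**The case against.** The case for leaving the rule alone has several sound parts. No decision turns on these rates: the primary test is unaffected and the safety outcomes are descriptive. Ending follow-up after explantation is a choice a sponsor could defend. The perioperative period, when deaths from conversion are most likely, is observed. The two intervals in the example overlap almost entirely. Section 8.3 defers complete methods to a Statistical Analysis Plan, which could specify censoring and so avoid a crude undercount.

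These arguments limit the size of the point but do not remove it. An analysis plan can choose a denominator or a censoring rule, but it cannot recover deaths or MAEs that were never collected, and censoring at conversion exit would probably be informative.

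A reader might go further than the text allows in five ways.
- **That the exit is caused by device failure.** Section 6.8 defines conversion by open repair with explantation and gives no cause. What the text supports is that conversion is a failure of the composite.
- **That converted subjects are the highest-risk group.** The background mortality figures make higher risk plausible, but the plan does not rank subjects by risk.
- **That the 12-month safety rates are biased downward as a matter of fact.** That depends on an unstated denominator rule and on whether unseen events occur.
- **That mortality and MAE are assigned to the modified intent-to-treat group.** Section 8.1 says only "Primary analyses will be performed on a modified intent-to-treat basis".
- **That every unseen MAE adds 1.3 points.** MAE is met by any one listed event. In a per-subject proportion, a later event adds nothing for a subject who already had one.

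The all-cause mortality definition is also ambiguous for a subject who has exited, since it refers to the study period. That is a reason to clarify it, not proof of a contradiction.

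**Conclusion.** The point holds as a mismatch between a stated follow-up rule and a stated reporting horizon. Followed as written, sections 6.8 and 6.15 leave deaths and first MAEs uncollected up to day 365 in subjects converted before about day 335, assuming discharge within 30 days. The loss is probably informative. The descriptive 12-month mortality and MAE rates may be understated if these subjects are counted as event-free.

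The upper limit of 1.3 to 4.0 points rests on an assumed 1 to 3 early conversions among 75, each with an unseen event. The likely effect is well below that. It is a modest safety-reporting gap, worth closing because it is cheap to close and cannot be repaired after the study.

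**What to change.** Amend sections 6.8 and 6.15 so that converted subjects remain in the study through 12 months for vital status and MAE collection, by phone contact or record check and without study imaging. State that they stay in the 12-month mortality and MAE denominators. Report the number converted and the number whose 12-month status is unknown.

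While amending, align the scope of the two sections. Section 6.8 describes conversion in an implanted subject with explantation, while section 6.15 also covers conversion at the initial procedure. It should be clear to whom the follow-up rule applies.

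The cost is amendment wording and a few contacts in what should be very few subjects. The downside for the sponsor is that reported 12-month safety rates may be slightly higher.

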### **6.9 Imaging Assessment**

The Sponsor will utilize an independent imaging Core Lab to analyze device performance specifically related to study endpoints such as: device integrity, endoleaks, migration, and aneurysm dimensions (e.g., length, diameter, volume). Clinical sites will submit all X-ray (KUB) and CT images to the Core Lab for all required study visits.

Study Visit	Images* Required to be submitted to Sponsor
Baseline	Contrast Enhanced Spiral Abdominal/Pelvic CT
Pre-Discharge	X-ray (KUB) (AP, lateral, left oblique and right oblique views)
1 month	Contrast Enhanced Spiral Abdominal/Pelvic CT X-ray (KUB) (AP, lateral, left oblique and right oblique views)
6 month	Contrast Enhanced Spiral Abdominal/Pelvic CT X-ray (KUB) (AP, lateral, left oblique and right oblique views)
12 month	Contrast Enhanced Spiral Abdominal/Pelvic CT

	X-ray (KUB) (AP, lateral, left oblique and right oblique views)
--	-----------------------------------------------------------------

\*Refer to **Appendix V: CT Scanning Techniques** for imaging requirements.

